7.9.12. Treatment Administration

On Day 1, after completing all the required assessments, the following will occur:

- Study medication will be prepared by the pharmacist/coordinator. (refer to the Pharmacy Binder for FX006 dose preparation instructions.)
- Synovial fluid will be aspirated from each knee just prior to administration of study medication (refer to Section [7.9.10](#) for more details of the synovial fluid aspiration).
- The injector/aspirator will perform the IA injection of the study medication (refer to Section [7.5.9](#) for instructions).

7.9.13. Review of Adverse Events and Concomitant Medications

After receiving assigned study medication, the patient will be monitored for any AEs. Review of any Concomitant Medications will also be performed and documented in source documentation. Refer to Section [8.1](#) for further information in regards to reporting of AEs. Refer to Section [7.6](#) for further information in regards to allowed and restricted concomitant medication.

8. CLINICAL SAFETY ASSESSMENTS

Safety evaluations will be based on the assessment of AEs occurring after the administration of study medication on Day 1 through the Final Visit (scheduled for Day 43). Results of clinical safety assessments are to be recorded in the patient's medical records and transcribed to the appropriate eCRF, including the AE eCRF for clinically significant findings.

8.1. Adverse Events

8.1.1. Definitions

An AE is any untoward medical occurrence in a patient or clinical investigation subject administered a pharmaceutical product and that does not necessarily have a causal relationship with this treatment.

An AE can therefore be:

- Any unfavorable and unintended sign (including an abnormal laboratory finding), symptom, or disease temporally associated with the use of a medicinal (investigational) product, whether or not related to the medicinal (investigational) product.
- Any clinically significant abnormality found on an ECG, laboratory test or physical examination.
- Any worsening (i.e., any clinical significant adverse change in frequency and/or intensity) of a preexisting condition, which is temporally associated with the use of the medicinal (investigational) product, is also an AE.

An SAE is any untoward medical occurrence that at any dose:

- Results in death,
- Is life-threatening,
 - This serious criterion refers to an event in which the patient was at substantial risk of death at the time of the event; it does not refer to an event which hypothetically might have caused death if it were more severe.
- Requires inpatient hospitalization or prolongation of existing hospitalization,
 - This serious criterion applies if the reported AE requires at least a 24-hour inpatient hospitalization or, if in the opinion of the Principal Investigator, prolongs an existing hospitalization. A hospitalization for an elective procedure or a routinely scheduled treatment is not an SAE by this criterion because a "procedure" or a "treatment" is not an untoward medical occurrence.
- Results in permanent or significant disability/incapacity, or
 - This serious criterion applies if the "disability" caused by the reported AE results in a substantial disruption of the patient's ability to carry out normal life functions.

- Is a congenital anomaly/birth defect.
 - This serious criterion applies if a patient exposed to a medicinal (investigational) product gives birth to a child with congenital anomaly or birth defect.
- Is, in the judgement of the PI, an important medical event. Medical and scientific judgment should be exercised in deciding that a medical event, although not immediately life-threatening, resulting in hospitalization, or in death is, nevertheless, clinically important and serious based on because the patient was in jeopardy of or require intervention to prevent one of the other outcomes listed above. Examples of such events are intensive treatment in an emergency room or at home for allergic bronchospasm; convulsions that do not result in hospitalization; or development of drug dependency or drug abuse.

8.1.2. Evaluating and Recording of Adverse Events

At each visit all AEs that occur from the time of treatment and throughout a patient's study participation that are observed, elicited by the site personnel, or reported by the patient, will be recorded in the source documentation and appropriate section of the AE eCRF and evaluated by the Principle Investigator or Sub-Investigator.

Minimum information required for each AE includes type of event, duration (start and end dates), severity, seriousness, causality to investigational medicinal product, action taken, and outcome.

Severity of AEs will be graded by the Principal Investigator using the Common Terminology Criteria for AEs (CTCAE) version 4.0 (refer to the Study Manual or http://ctep.cancer.gov/protocolDevelopment/electronic_applications/ctc.htm).

For AEs not listed in the CTCAE, the following definitions should be used:

| | |
|---------|---|
| Grade 1 | Mild Symptomatic or mild symptoms Clinical or diagnostic observations only Intervention not indicated |
| Grade 2 | Moderate Minimal, local or noninvasive intervention indicated Limiting age-appropriate instrumental activities of daily living (ADL)* |
| Grade 3 | Severe or medically significant but not immediately life-threatening Hospitalization or prolongation of hospitalization indicated Disabling Limiting self-care ADL** |
| Grade 4 | Life-threatening consequences Urgent intervention indicated |
| Grade 5 | Death related to AE |

*Instrumental ADL refer to preparing meals, shopping for groceries or clothes, using the telephone, managing money, etc.

**Self-care ADL refer to bathing, dressing and undressing, feeding self, using the toilet, taking medications, and not bedridden.

The relationship of the AE to the investigational medicinal product should be specified by the Principal Investigator, using the following definitions:

1. Not Related: Concomitant illness, accident or event with no reasonable association with treatment.
2. Unlikely: The reaction has little or no temporal sequence from administration of the investigational medicinal product, and/or a more likely alternative etiology exists.
3. Possibly Related: The reaction follows a reasonably temporal sequence from administration of the investigational medicinal product and follows a known response pattern to the suspected drug; the reaction could have been produced by the study medication or could have been produced by the subject's clinical state or by other modes of therapy administered to the subject.
4. Probably Related: The reaction follows a reasonable temporal sequence from administration of study medication; is confirmed by discontinuation of the study medication or by rechallenge; and cannot be reasonably explained by the known characteristics of the subject's clinical state.
5. Definitely Related: The reaction follows a reasonable temporal sequence from administration of study medication; that follows a known or expected response pattern to the study medication; and that is confirmed by

improvement on stopping or reducing the dosage of the study medication, and reappearance of the reaction on repeated exposure.

If discernible at the time of completing an AE eCRF, a specific disease or syndrome rather than individual associated signs and symptoms should be identified by the Investigator and recorded on the appropriate AE eCRF. However, if an observed or reported sign, symptom, or clinically significant laboratory anomaly is not considered by the Investigator to be a component of a specific disease or syndrome, then it should be recorded as a separate AE on the appropriate AE eCRF.

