7.5.11. Removal of Patients from Therapy or Assessments

Each treated patient in this study receives study medication as a single IA injection. Therefore, discontinuation from treatment is not applicable. Each patient may only discontinue from the study for further assessments and study visits.

Each patient will be informed of his/her right to discontinue from the study at any time for any reason and without prejudice to alternative treatment. The Principal Investigator may also discontinue a patient from the study at any time if, for example, he/she considers the patient's health to be compromised by remaining in the study, or the study is prematurely terminated. In these cases the Principal Investigator will:

1. Attempt to arrange for a formal Early Termination Visit and complete the study assessments specified for the End-of-Study Visit (Day 43).
2. Determine whether the patient is willing to be contacted to follow ongoing or new AEs through Day 43 (if reason for discontinuation is not "subject withdrew consent")
3. Document patient consent in the source document for continued follow-up.
4. Contact the patient as necessary (via phone or in-person) to follow ongoing or new AEs through Day 43 (concomitant medications associated with any AE will also be captured).

Data collected from discontinued patients will be included in the clinical study report. Patients who discontinue from the study may be replaced at the discretion of the Sponsor.

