8.1.3. Reporting of Serious Adverse Events

When an SAE occurs, the Investigator or designee, must log into the electronic data capture (EDC) system and complete the SAE report form within 24 hours of first becoming aware of the SAE. The SAE will automatically be reported to the Medical Monitor, or designee, electronically.

Follow up information relating to an SAE must be reported to the Medical Monitor, or designee, within 24 hours of receipt by the Investigator by entering new information into the electronic SAE form. The updated SAE will be automatically reported to the Medical Monitor or designee electronically.

If one is unable to log into the EDC system, the SAE hotline may be contacted (information located in the Investigator Site File in the Study Contact List).

All SAEs that occur at your site should, in addition, be reported by the Investigators to the responsible IRB/EC without undue delay, if applicable according to IRB/EC requirements.

During the conduct of the study, the Sponsor will provide expedited safety reports (AEs classified as serious, unexpected and at least possibly related to investigational product) to the investigative sites as notification of new safety findings. If this occurs, the investigative site must report the information to their IRB/EC per local guidelines (may be submitted by the Sponsor or designee for sites that use a central IRB).

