Similar data presentations will be made for knee related TEAEs. In these tabulations, related is defined as any TEAE deemed possibly, probably or definitely related to study drug by the investigator.

Tabulations presented in SOC internal agreed order and PT in alphabetical order within each SOC will also be produced for:

- all treatment-emergent AEs
- related TEAEs
- TEAEs by maximum severity
- for serious TEAEs

Knee related TEAEs will be tabulated in a similar manner. Knee related TEAEs that occur in both knees will be provided in a separate listing.

No formal hypothesis-testing analysis of AE incidence rates will be performed.

All AEs occurring on-study will be provided in data listings.

By-patient listings will also be provided for the following: patient deaths, Serious Adverse Events (SAE), and AEs leading to discontinuation.

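### The Protocol 8.1.2 causality grades do not fit one-visit dosing, and a reaction with plausible timing, no likelier cause and no known pattern has no valid grade

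*Protocol*

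**What the plan says.** Protocol 8.1.2 has causality assigned from a fixed list: "The relationship of the AE to the investigational medicinal product should be specified by the Principal Investigator, using the following definitions". The five grades are:

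- Not Related: "Concomitant illness, accident or event with no reasonable association with treatment".
- Unlikely: weak or absent timing, or a likelier other cause, or both.
- Possibly Related: plausible timing, and the event "follows a known response pattern to the suspected drug". A closing clause adds that the drug, the patient's condition or another therapy could have produced it.
- Probably Related: plausible timing, no reasonable explanation in the patient's condition, and the reaction "is confirmed by discontinuation of the study medication or by rechallenge".
- Definitely Related: plausible timing, a known or expected pattern, and "improvement on stopping or reducing the dosage of the study medication, and reappearance of the reaction on repeated exposure".

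On dosing, each knee is injected once at the same visit, the second within 15 minutes of the first (Protocol 7.5.9, SAP 2.3). Protocol 7.5.11 draws the consequence: "Therefore, discontinuation from treatment is not applicable". SAP 2.3 and 4.2.7 say the same, and 2.3 makes an exception for a patient with only one knee injected. Protocol 7.6.2 restricts intra-articular corticosteroids in any joint from consent to the End of Study visit.

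The grade is then used in two places. Under Protocol 8.1.3 the sponsor's expedited reports to sites cover "AEs classified as serious, unexpected and at least possibly related to investigational product". In SAP 4.9.1, "related is defined as any TEAE deemed possibly, probably or definitely related to study drug by the investigator".

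**The concern.** The scale reads as if written for a drug that can be stopped and restarted. Its two upper grades turn on dechallenge or rechallenge, which this plan does not provide for. The one related grade that remains asks for a pattern already known. A genuinely new reaction is therefore the kind of event the scale handles worst.

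That matters here because safety and tolerability is one of the two primary objectives (Protocol 6.1), injection of both knees is described as not yet studied (Protocol 5.2.1), and the stated purpose includes establishing safety at higher plasma levels (Protocol 7.3.1). With about 12 patients per arm and no formal testing of adverse events (SAP 4.9.1), the safety conclusion depends heavily on how single events are described and classified. At stake are the content of the related-TEAE tables (SAP Tables 14.3.1.3 and 14.3.1.6), the spread of events across grades in the by-relationship summary, and the trigger for expedited notices to sites.

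**Working it through.** The plan gives no figure to reproduce. The check sets each grade's conditions against the dosing and then against the uses made of the grade.

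**Step 1: is dechallenge available?** Both documents say stopping treatment does not apply. The only stopping foreseen is an injection halted before the full volume is in (Protocol 7.5.10) or, by implication, a second knee left uninjected (SAP 2.3). Either might be argued to be dechallenge for a reaction during the procedure. Neither removes drug already in a joint, and neither helps with a reaction that starts later.

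**Step 2: is rechallenge available?** No further dose is scheduled, and Protocol 7.6.2 restricts intra-articular corticosteroids to the end of the study. The plan provides for no rechallenge.

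**Step 3: grade a test reaction.** Take a reaction with plausible timing after dosing, no likelier cause and no known response pattern.

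| Grade | Deciding condition | Does the test reaction meet it? | Counted as related (SAP 4.9.1) |
|---|---|---|---|
| Not Related | No reasonable link with treatment | No, the timing is plausible | No |
| Unlikely | Poor timing or a likelier cause | No, neither is present | No |
| Possibly | Plausible timing and known pattern | No, the pattern is missing | Yes |
| Probably | Dechallenge or rechallenge | No, neither is available | Yes |
| Definitely | Known or expected pattern, dechallenge and rechallenge | No, all three are missing | Yes |

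Probably Related carries no known-pattern condition. The test reaction is shut out of it only because stopping and re-exposure are unavailable.

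**Step 4: count.** There are 5 grades, of which 3 count as related. Grades that need dechallenge or rechallenge: 2. Related grades left: 3 − 2 = 1. Related grades open to the test reaction: 0 of 3. Unrelated grades that fit it: 0 of 2. It fits 0 of 5.

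**Step 5: repeat for a reaction with a known pattern.** It meets Possibly Related and counts as related. Only the distinction between Possibly, Probably and Definitely is lost.

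**Step 6: would a looser reading rescue the upper grades?** Suppose discontinuation were taken to mean the drug wearing off. FX006 is intended to deliver drug for about 3 months (Protocol 5.2.1), while follow-up ends at Day 43, so release would normally outlast observation. TAcS is immediate-release. Probably Related could then be easier to reach in the reference arm than in the test arm, in an open-label comparison.

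**Step 7: follow the grade downstream.** The expedited rule needs an event that is both unexpected and at least possibly related. If it is unexpected because it matches no known pattern, the Possibly Related definition and the rule pull against each other. The related-TEAE tables take only the three upper grades, so an event without a valid grade has no assured place in them.

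**The case against.** The other side has real strength.

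First, the SAP pools the three upper grades. Losing Probably and Definitely changes no related/unrelated count for known-pattern events. This stands.

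Second, several safeguards do not depend on causality. Every SAE is entered within 24 hours of the site becoming aware of it and passes automatically to the Medical Monitor (Protocol 8.1.3), who must review all safety information promptly (8.1.4). SAEs also go to the IRB/EC where its requirements call for it. All TEAEs, knee-related TEAEs and SAEs are tabulated (SAP Tables 14.3.1.2, 14.3.1.5 and 14.3.1.8), and every on-study AE is listed. In an open-label study of about 24 patients, a new reaction would be visible. This also stands.

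Third, a reader might infer that the ungradeable reaction falls to Unlikely or Not Related and so is left out of the related tables. The documents do not say that. They give no default, and an investigator could choose Possibly Related on the strength of its closing clause or of judgement. The exclusion is a risk of inconsistent grading, not a stated outcome.

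Fourth, the expedited-reporting conflict is narrower than it looks. Protocol 8.1.3 neither defines unexpected nor says who decides relatedness for this purpose. An event new to FX006 but typical of a corticosteroid could be graded Possibly Related and reported. With 687 patients already treated with FX006 (Protocol 5.2.7), events with no recognisable pattern may be few, though the documents give no estimate. The conflict survives for that class.

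Fifth, the halted-injection and one-knee cases mean it is too strong to say that the upper grades are closed to every patient. That is conceded, as a narrow exception.

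**Conclusion.** The point holds as an inconsistency within the protocol that should be corrected, short of a critical flaw. Two of five grades cannot be applied as written in either arm, apart from the narrow exception in Step 1. This does not depend on FX006 being a depot: TAcS is also given once. For a reaction with plausible timing, no likelier cause and no known pattern, none of the three related grades fits and neither do the other two. Such an event may be missed from the related-TEAE tables and from expedited notices to sites.

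A reader might go further and conclude that new reactions would be lost or that the safety objective fails. The documents do not support that: the event stays in the overall TEAE tables and listings and, if serious, in the SAE outputs and before the Medical Monitor.

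The conclusion rests on three assumptions: investigators apply the definitions literally, as 8.1.2 instructs; no separate sponsor causality assessment exists, since none is described; and the SAP's meaning of related, which is worded next to the knee-related summaries, governs both related-TEAE tables. How many events would be affected cannot be estimated from the documents.

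**What to change.** Reconcile Protocol 8.1.2 with 7.5.11 and 8.1.3 and with SAP 4.9.1, in the protocol text and the eCRF completion guidance:

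1. Possibly Related: remove the known response pattern as a requirement, so that plausible timing and a possible role for study drug suffice.
2. Probably and Definitely Related: make dechallenge and rechallenge supporting evidence where applicable, not a condition. Let the grades rest on timing, pharmacological or local plausibility, and the absence of a likelier cause.
3. Keep the SAP rule that pools the three grades as related.

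The cost is protocol and guidance wording and a note to sites. No dose, visit, sample or patient number changes. The downside is that some more events may be graded related, and in an open-label study a looser threshold could make the related/unrelated split somewhat less informative. The tables of all TEAEs are unaffected.

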8.1.3. Reporting of Serious Adverse Events

When an SAE occurs, the Investigator or designee, must log into the electronic data capture (EDC) system and complete the SAE report form within 24 hours of first becoming aware of the SAE. The SAE will automatically be reported to the Medical Monitor, or designee, electronically.

Follow up information relating to an SAE must be reported to the Medical Monitor, or designee, within 24 hours of receipt by the Investigator by entering new information into the electronic SAE form. The updated SAE will be automatically reported to the Medical Monitor or designee electronically.

If one is unable to log into the EDC system, the SAE hotline may be contacted (information located in the Investigator Site File in the Study Contact List).

All SAEs that occur at your site should, in addition, be reported by the Investigators to the responsible IRB/EC without undue delay, if applicable according to IRB/EC requirements.

During the conduct of the study, the Sponsor will provide expedited safety reports (AEs classified as serious, unexpected and at least possibly related to investigational product) to the investigative sites as notification of new safety findings. If this occurs, the investigative site must report the information to their IRB/EC per local guidelines (may be submitted by the Sponsor or designee for sites that use a central IRB).

8.1.4. Safety Monitoring Roles

The site personnel will carefully monitor each patient throughout the study for possible AEs. All AEs will be documented on the eCRF designed specifically for this purpose, and will be followed until either completely resolved or until a stable chronic outcome is determined by the Principal Investigator. SAEs will be reported in accordance with Section 8.1.3.

The Medical Monitor must promptly review all information relevant to the safety of an investigational new product received from any source. The Medical Monitor will also review alert laboratory results in real time and will contact Investigators as needed to ensure that issues are managed in an appropriate manner.

8.1.5. Clinical Management of Knee-related Events

In the event that the patient has an immediate reaction following administration of study medication or returns to the clinic with an acute exacerbation (e.g., tenderness, increased pain,

swelling, effusion, decreased mobility of the knee), the patient should be treated according to local clinical guidelines and physician experience.

If the knee is aspirated at any time after administration of study medication for any reason, the volume of synovial fluid aspirated must be documented, synovial fluid should be (1) cultured, (2) evaluated for presence of crystals and (3) assessed for white cell count at a local laboratory, and the results should be documented.

Any event that is a change from the patient's baseline status (new or worsening case) should be reported as an AE and those meeting the definition of serious must be reported in accordance with Section [8.1.3](#).

